6.2.3 Identification of other outcomes

Secondary and exploratory objectives, described further in Sections 0 and 0 respectively, include the following outcomes:

- HZO during the follow-up period will be identified using natural language processing (NLP) of EHR notes, as described in our previous study [36].
- Hospitalized AMI will be identified by ICD-10 codes from inpatient encounters, or Emergency Department encounters if the patient was hospitalized or if the patient died the same or next day.
- Hospitalized stroke will be identified by ICD-10 codes from inpatient encounters, or Emergency Department encounters if the patient was hospitalized or if the patient died the same or next day.
- Characteristics of the clinical presentation of the initial acute HZ episode will be identified from chart review.
- HZ-related meningoencephalitis will be identified by targeted chart review of inpatient encounters with ICD-10 codes and/or cerebrospinal fluid (CSF) test results positive for VZV.
- HZ-related bacterial superinfection will be identified by ICD-10 codes and antibiotic prescriptions.
- Disseminated HZ will be identified by targeted chart review of EHR of vaccinated and unvaccinated individuals who are immunocompromised at the time of their incident HZ diagnosis.

6.3 Other Variable Definitions

Other variables will be identified from EHRs and considered in analyses when appropriate as covariates or stratification variables, including:

- Demographic variables: age at index date, sex, race/ethnicity
- Health care utilization (number of outpatient/emergency/inpatient encounters) in year prior to index date
- Comorbidities (*e.g.*, kidney disease, heart disease, lung disease [*i.e.*, chronic obstructive pulmonary disease], liver disease, diabetes) in year prior to index date
- Immunocompromised status during follow-up (time-varying). Immunocompromised status will be identified from ICD-10 codes of immunocompromising conditions and pharmacy dispense data of immunosuppressing medications
- History of ZVL prior to index date based on dates of vaccinations in the EHR
- History of HZ prior to index date identified using ICD-10 codes (B02.xx) and ICD-9 codes (053.xx) from hospital, outpatient, and Emergency Department settings
- Concomitant vaccinations at time of exposure (*e.g.,* receipt of influenza vaccine, pneumococcal vaccine or Tdap)

Kaiser Permanente **Research**

7. STUDY POPULATION

7.1 Eligibility Criteria

Individuals will be eligible for inclusion in the study if the following criteria are met:

- Age 50 years or more at the index date for all study objectives
- At least 1 year of continuous KPSC membership before the index date (allowing for a 31-day gap in membership)

Certain individuals will be excluded from the study. Individuals who receive a second dose less than 4 weeks after the first dose will be excluded, since ACIP guidelines state that these individuals must repeat the second dose. Individuals with an HZ diagnosis in the 6 months prior to index date will be excluded to ensure that HZ diagnoses after index date are new, rather than carried over from HZ episodes prior to index date. Individuals with HZ occurring within 30 days after the index date for both exposed and unexposed groups will also be excluded since it is unclear if HZ began before or after index date and whether the length of time since vaccination (for RZV vaccinated individuals) is long enough to allow development of immunity.

Individuals with immunocompromising conditions (*e.g.,* leukemia, lymphoma, human immunodeficiency virus) or who received immunosuppressant agents in the year prior to index date will not be excluded from the study, but VE estimates will be adjusted for time-varying immunocompromised status (Section 0).

The 1-dose RZV cohort will consist of eligible individuals who receive 1 dose of RZV. Such individuals may go on to receive a second RZV dose within 4 weeks to 6 months of the first dose, a second RZV dose >6 months after the first dose, or no subsequent RZV doses. The index date for the 1-dose RZV cohort will be the date of the first dose of RZV. RZV unvaccinated individuals corresponding to the 1-dose RZV cohort will be randomly selected from the RZV unvaccinated population and up to 4:1 matched to the 1-dose RZV vaccinated individuals by age and sex. *Further matching will be done on race/ethnicity (White, Black, Hispanic, Asian, and Other) if 95% of exposed individuals can be fully matched to 4 unexposed individuals. (Amended 17 February 2022.)* The index date for the 1-dose RZV unvaccinated match will be the same as his/her matched 1-dose RZV counterpart. The same unvaccinated individual can be matched to both an individual in the 2-dose (4 weeks to 6 months) RZV cohort and an individual in the 1-dose RZV cohort. This increases the likelihood of being able to find an appropriate RZV unvaccinated match.

The 2-dose (>6 months) RZV cohort will comprise individuals who receive a second dose of RZV more than 6 months after the first dose. The date of the second RZV dose will be considered the index date. These individuals will retain the same unvaccinated matches that they had in the 1-dose RZV cohort. This is because the interval between the first dose and the second dose is unpredictable and could be very long (e.g. years), and it would not be feasible to indefinitely extend the study in order to match and follow-up these individuals. Some of the unvaccinated matches to the 1-dose RZV cohort may experience a censoring event (i.e., unvaccinated match receives RZV, terminates membership, dies, or develops the event of interest) and will no longer be available as an unvaccinated match at the time of the second RZV dose (>6 months) index date. These unvaccinated matches will not be replaced, so the matching ratio for the 2-dose (>6 months) RZV cohort will be less than 4:1.

Individuals will be followed for 10 years. For individuals and their matches in the 2-dose (4 weeks to 6 months) RZV cohort, this will be 10 years after the date of the second dose. For individuals in the 1-dose RZV cohort or 2-dose (>6 months) RZV cohort, this will be 10 years after the date of the first dose. Follow-up will end upon the occurrence of a censoring event (i.e., death, termination of KPSC membership (allowing for a 31-day gap in membership), or occurrence of event of interest (for event-specific analyses), whichever comes first.

Individuals in the 1-dose RZV cohort and their unvaccinated matches will contribute person-time to the 1-dose cohort until they receive an RZV dose, reach the end of follow-up, or experience a censoring event (i.e., termination of membership, death, or development of event of interest), upon which time they will stop contributing person-time to the 1-dose RZV cohort. Individuals who receive a second dose 4 weeks to 6 months after the first dose will enter the 2-dose (4 weeks to 6 months) RZV cohort, and they will receive new independently-selected unvaccinated matches, as described for the 2-dose (4 weeks to 6 months) RZV cohort above. Individuals who receive a second dose more than 6 months after the first dose will enter the 2-dose (26 months) RZV cohort, but they will keep the same matches that they had in the 1-dose RZV cohort. However, only person-time contributed after the date of the second dose (>6 months) for vaccinated individuals and their unvaccinated matches will be included in the 2-dose (>6 months) analyses.

Kaiser Permanente **Research**

Figure 1. Construction of study cohorts (Amended 17 February 2022)

Kaiser Permanente **Research**

8. ANALYSIS

8.1 Primary Analyses

We will describe and compare the number and characteristics of individuals in each cohort. Categorical variables such as those listed in Section 0 will be presented as absolute numbers and percentages with p-values for the χ^2 test. Continuous variables such as age in years will be presented as the mean with standard deviation and/or median with interquartile ranges, with p-values for the two-sample t-test or Wilcoxon rank-sum test, as appropriate. Overall incidence rates of HZ for 2-dose (4 weeks to 6 months) RZV vaccinated cohort and the matched unvaccinated cohort will be calculated by dividing the number of HZ cases by the total number of person-years.

To calculate the crude VE by follow-up year after vaccination, the number of HZ cases occurring within that year and the number of person-years of follow-up for subjects in that year will be assessed for the 2-dose (4 weeks to 6 months) RZV cohort and the matched unvaccinated cohort. Crude VE (%) will be estimated as (1 – [incidence rate of HZ among 2-dose (4 weeks to 6 months) RZV recipients / incidence rate of HZ among RZV unvaccinated individuals]) x 100.

Adjusted hazard ratios (HRs) and 95% confidence intervals (Cls) comparing HZ incidence rates in the 2dose (4 weeks to 6 months) RZV cohort and the matched unvaccinated cohort will be estimated by Cox proportional hazards regression models adjusting for potential confounders (Section 0). If the vaccine effect wanes over time and the proportional hazard assumption does not hold, time-varying Cox regression models which model the risk of HZ by time interval will be used to estimate the adjusted HRs and 95% Cls. Estimates of VE (%) will be calculated as (1 – adjusted HR) × 100. Competing risks such as death will be assessed and will be accounted for in the analyses as appropriate.

Similarly, to calculate the crude VE for preventing PHN by follow-up year after vaccination, the number of PHN cases occurring within that year and the number of person-years of follow-up for subjects in that year will be assessed for the 2-dose (4 weeks to 6 months) RZV cohort and the matched unvaccinated cohort. Crude VE (%) will be estimated as (1 – [incidence of PHN among the 2-dose (4 weeks to 6 months) RZV vaccine recipients / incidence of PHN among RZV unvaccinated individuals]) x 100. The adjusted HRs and 95% CIs comparing PHN incidence in the 2-dose (4 weeks to 6 months) RZV cohort and the matched unvaccinated cohort will be estimated by Cox proportional hazards regression models adjusting for potential confounders (Section 0). In addition, for primary objective 2, adjusted relative risks for PHN among HZ cases that were 2-dose (4 weeks to 6 months) RZV vaccine recipients compared to RZV unvaccinated HZ cases will be calculated using Poisson regression with robust error variance [37]. Matching will be broken for this analysis.

8.2 Secondary Analyses

Analyses will be conducted to address the secondary objectives described in Section 3. Matched sets will not be maintained in stratified analyses (except in stratified analyses by age, by sex, **and by race/ethnicity) (Amended 17 February 2022)**; therefore, matching variables will be adjusted in the Cox proportional hazards regression models.

Secondary objectives 1 and 2: The primary analyses for HZ and PHN comparing the 2-dose (4 weeks to 6 months) RZV cohort with the matched unvaccinated cohort will be stratified by age at index date (50-59, 60-69, 70-79, ≥80 years), by sex, and by race / ethnicity. For each stratum, we will calculate HZ incidence and PHN incidence, adjusted HRs and 95% CIs, and VE (Section 0).

Secondary objective 3 and 4: The primary analyses for HZ comparing the 2-dose (4 weeks to 6 months) RZV cohort with the matched unvaccinated cohort will be stratified by (a) each of the following comorbidities in the year prior to index date: kidney disease, heart disease, lung disease, liver disease, diabetes and (b) history of ZVL prior to the index date. For each stratum, we will calculate HZ incidence, adjusted HRs and 95% CIs, and VE. The methods will be similar to those used in the primary analyses (Section 0).

Secondary objective 5: We will describe HZ incidence in the 2-dose (4 weeks to 6 months) RZV cohort and the matched unvaccinated cohort, stratified by history of HZ (defined as any diagnosis of HZ 6 months prior to the index date).

Secondary objective 6: We will assess the VE of 2 doses of RZV (among the 2-dose (4 weeks to 6 months) RZV cohort) in preventing HZO. Individuals with HZO in the 6 months prior to the index date will be excluded and the first occurrence after index date will be identified. Analyses will use similar methods to the primary analyses (Section 0).

8.3 Exploratory Analyses

Exploratory objective 1: We will estimate the VE of RZV in preventing HZ and PHN in adults aged \geq 50 years who completed 2 doses of the vaccine, but the second dose was received more than 6 months after the first dose (2-dose (>6 months) RZV cohort). The date of the second RZV dose will be the index date. We will use a similar analysis approach as was described for the primary objectives in Section 0.

Exploratory objective 2: We will assess VE of 2 doses of RZV (among the 2-dose (4 weeks to 6 months) RZV cohort) with concomitant vaccination (*e.g.*, receipt of influenza vaccine, pneumococcal vaccine, or Tdap) at the time of receiving either the first or second dose of RZV in preventing HZ in adults aged \geq 50 years. We will compare HZ incidence in individuals who received 2 doses of RZV and received another vaccine on the same day as either the first or second dose of RZV with RZV unvaccinated individuals. We will also compare the HZ incidence in individuals who received 2 doses of RZV and did not receive another vaccine on the same day as both the first and second dose of RZV with RZV unvaccinated individuals. For each of these analyses, we will estimate adjusted HRs and 95% CIs, and VE using methods similar to those described in Section 0.

Exploratory objective 3: We will conduct chart reviews to assess clinical characteristics related to the initial acute HZ episode for a sample of cases (100 2-dose (4 weeks to 6 months) RZV vaccinated HZ cases and 100 unvaccinated HZ cases). We will abstract clinical characteristics on the HZ episode from medical encounters 30 days before and after the initial HZ diagnosis, including: date of rash onset, date of HZ diagnosis, number of days from onset of rash to HZ diagnosis, affected dermatomes, location of rash, rash characteristics, severity of HZ, complications related to acute HZ, whether there was a positive test result for VZV (if available), specialty of provider making diagnosis, and antiviral prescription information. Clinical characteristics for vaccinated and unvaccinated cases will be presented as absolute numbers and percentages with p-values for the χ^2 test (categorical variables) or mean with standard deviation and/or median with interquartile ranges, with p-values for the two-sample t-test or Wilcoxon rank-sum test (continuous variables).

Exploratory objective 4: We will assess VE of 2 doses of RZV in preventing HZ-related meningoencephalitis and HZ-related bacterial superinfection in adults aged \geq 50 years. For both meningoencephalitis and bacterial superinfection outcomes (Section 6.2.3), the first occurrence after index date will be identified. Analyses will use similar methods to the primary analyses (Section 0).

Exploratory objective 5: We will conduct chart reviews for disseminated HZ among a sample of HZ cases with immunocompromised status at the time of HZ diagnosis (Section 6.2.3) (up to 100 2-dose (4 weeks to 6 months) RZV vaccinated HZ cases and 100 unvaccinated HZ cases per year for 10 years). We will calculate the relative risk of disseminated HZ between these two groups.

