Recombinant zoster vaccine (SHINGRIX, RZV), a two-dose subunit zoster vaccine containing recombinant glycoprotein E in combination with a novel adjuvant (AS01_B), was licensed by the FDA in 2017. This decision was based on two large parallel Phase III randomized controlled trials (RCTs): the Zoster Efficacy Study in Adults 50 Years of Age or Older (ZOE-50) and the Zoster Efficacy Study in Adults 70 Years of Age or Older (ZOE-70). ZOE-50 assessed whether RZV reduced the risk of HZ in adults 50 years of age or older. During a mean follow-up of 3.2 years, HZ was confirmed in 6 out of 7,698 participants in the vaccine group and in 210 out of 7,713 participants in the placebo group (incidence rate 0.3 vs. 9.1 per 1,000 person-years). Overall vaccine efficacy against HZ was 97.2% and ranged between 96.6% and 97.9% for all age groups evaluated [15]. In ZOE-70, the overall vaccine efficacy against HZ was 89.8% (6,541 vaccinated participants and 6,622 placebo participants) and was similar in participants 70-79 years of age (90.0%) and participants 80 years of age and older (89.1%) [16]. Although these Phase III RCTs were not powered to show statistical significance in serious adverse events, there were no observed differences between subjects vaccinated with RZV and comparison populations for the overall reported rates of serious adverse events [15]. Per indication, RZV is not contraindicated in persons with immunosuppressive conditions or treatments. Subsequent to FDA approval, ACIP made three recommendations: (1) RZV is recommended for immunocompetent adults aged 50 years and older; (2) RZV is recommended for immunocompetent adults previously vaccinated with ZVL; and (3) RZV is the preferred vaccine over ZVL [9].

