- To estimate the VE of 2 doses of RZV in preventing HZ, by presence of concomitant vaccination (*e.g.,* receipt of influenza vaccine, pneumococcal vaccine, or tetanus, diphtheria and pertussis vaccine [Tdap]) at the time of receiving either the first or second dose of RZV) in adults aged ≥ 50 years

- 3. To assess clinical characteristics associated with the acute HZ episode for a sample of cases (100 RZV vaccinated [2-dose] HZ cases and 100 RZV unvaccinated HZ cases) in adults aged ≥ 50 years
- 4. To estimate the VE of 2 doses of RZV in preventing HZ-related meningoencephalitis and bacterial superinfection in adults aged ≥ 50 years
- To estimate the relative risk of disseminated HZ among vaccinated (2 doses of RZV) and RZV unvaccinated adults ≥ 50 years who are immunocompromised at the time of their incident HZ diagnosis

Kaiser Permanente **Research**

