8.4 Sample Size and Power Estimation

We computed the sample size needed to assess RZV effectiveness against HZ and PHN. We estimated that the incidence of HZ ranges from 10 to 15/1,000 person-years in the RZV unvaccinated group, and that the incidence of PHN ranges from 1.0 to 1.5/1,000 person-years in the RZV unvaccinated group, and the censoring rates in the RZV vaccinated and RZV unvaccinated groups are 7% and 15% per year, respectively. We expect a higher drop out over time in the RZV unvaccinated group due to receipt of RZV.

The sample size calculation was conducted using a two-sided log rank test with alpha=0.05, to achieve 80% statistical power, based on certain assumptions for incidence rate in the RZV unvaccinated group, follow-up period, censoring rate, matching ratio, and detectable HR (or VE). The calculation was performed using SAS software package (version 9.3) PROC POWER procedure.

Assumptions for sample size calculation:

- Incidence of HZ in the RZV unvaccinated group: 10, 12, 15/1,000 person-years
- Incidence of PHN in the RZV unvaccinated group: 1.0, 1.2, 1.5/1,000 person-years
- Follow-up period: 5 or 10 years after the second dose of RZV
- Censoring rate in the RZV vaccinated group: 7%
- Censoring rate in the RZV unvaccinated group: 15%
- Ratio of RZV unvaccinated to RZV vaccinated group: 4:1
- Detectable HR (or VE): 0.1, 0.2, 0.3, or 0.4 (VE=90%, 80%, 70%, or 60%)

Table 3 to Table 6 below present the sample size estimated to be sufficient to detect a HR of PHN and HZ between the vaccinated and unvaccinated cohorts with a follow-up period of 5 years (interim report) or 10 years (complete follow-up period). The study sample size is determined based on a conservative approach for subgroup analysis of VE against PHN. Given a PHN incidence of 1/1,000 person-years in the RZV unvaccinated group, application of censoring rates in the RZV vaccinated and RZV unvaccinated groups, and 5 years of follow-up, we need 5,836 patients with completion of two doses of RZV for a subgroup analysis to achieve 80% of power of detecting a HR of 0.4 (60% VE).

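### Exploratory objective 3 compares acute HZ severity and complications between 100 vaccinated and 100 unvaccinated cases without adjustment, so an age difference between the two sets of cases could confound the comparison

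*Supplement*

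**What the plan says.** Section 3 words the objective descriptively: "To assess clinical characteristics associated with the acute HZ episode for a sample of cases". Section 8.3 sets the sample at "100 2-dose (4 weeks to 6 months) RZV vaccinated HZ cases and 100 unvaccinated HZ cases". The items abstracted from the charts include "rash characteristics, severity of HZ, complications related to acute HZ".

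For the comparison, section 8.3 states: "Clinical characteristics for vaccinated and unvaccinated cases will be presented as absolute numbers and percentages with p-values". The tests are chi-square for categorical items and a t-test or Wilcoxon test for continuous ones. It mentions no covariate, no stratification and no rule for choosing the 200 cases.

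Three other places bear on this:

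- Section 7.2 matches the cohorts 4:1 on age and sex (and race/ethnicity where feasible) at the index date.
- Section 8.1, for primary objective 2, also compares vaccinated with unvaccinated HZ cases, on the risk of PHN. It breaks the matching and plans adjusted relative risks from robust-variance Poisson regression.
- Section 11 says it is not known whether vaccination produces modified or atypical HZ.

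**The concern.** Cohort matching equalises the people at risk. The cases are a selected subset, and in the vaccinated arm the selection runs through vaccine failure. If the vaccine protects older people less well, vaccinated cases will be older than unvaccinated cases even when the cohorts are perfectly matched. Any feature that depends on age then differs between the arms with no vaccine effect on the disease itself. Such a difference could make breakthrough HZ look worse than it is, or hide a real attenuation.

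Time since index could differ as well. Section 8.4 assumes 7% yearly censoring in the vaccinated arm and 15% in the unvaccinated arm, and explains: "We expect a higher drop out over time in the RZV unvaccinated group due to receipt of RZV". Unvaccinated cases would therefore tend to occur somewhat earlier in follow-up.

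The plan adjusts its closest parallel, PHN among HZ cases, but not this comparison, and gives no reason for the difference.

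**Working it through.** Section 8.3 gives no power, effect size or detectable difference for the 100 + 100 cases, so there is no stated figure to reproduce. The check asks how far the age mix of the cases could drift apart, and what the planned tests would then do.

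**Inputs from the protocol**

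- Age mix, Table 1 (membership as a stand-in for the cohort): 39.86%, 32.97%, 18.43% and 8.74% for 50-59, 60-69, 70-79 and 80+. Below 70: 72.83%. From 70: 27.17%.
- Efficacy, section 2. ZOE-50: 97.2% overall, 96.6% to 97.9% across age groups. ZOE-70: 89.8% overall, 90.0% at 70-79 and 89.1% at 80+.

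**Assumptions not in the protocol**

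- Baseline HZ incidence is flat in age, or rises as 0.7/1/1.3/1.4 over the four bands.
- The clinical feature occurs in 20% vs 30%, 20% vs 40%, or 10% vs 30% of cases below 70 vs from 70, identically in both arms.

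**Step 1: age mix of the cases.** Weight of an age band = age share × baseline incidence × (1 if unvaccinated, 1 − VE if vaccinated). For the cross-trial gradient with flat incidence:

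- Unvaccinated, 70+: 27.2%.
- Vaccinated, below 70: 72.83 × 0.028 = 2.039.
- Vaccinated, 70+: 18.43 × 0.100 + 8.74 × 0.109 = 2.796.
- Vaccinated share 70+: 2.796 / (2.039 + 2.796) = 57.8%.

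With band midpoints 55, 65, 75 and 85, mean age is about 70.4 in vaccinated and 64.6 in unvaccinated cases.

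**Step 2: spurious difference.** Difference in share aged 70+ × difference in age-specific rate. For the cross-trial gradient: (0.578 − 0.272) × 0.10 = 3.1 points, and × 0.20 = 6.1 points.

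**Step 3: false positives.** 20,000 simulated samples of 100 vs 100, no vaccine effect within age group (below 70, 70+), uncorrected chi-square at two-sided 5%.

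| Efficacy by age | Incidence | 70+ among vaccinated vs unvaccinated cases | Spurious difference (points, absolute) | False positives, plain test |
|---|---|---|---|---|
| Equal at all ages | flat | 27.2% vs 27.2% | 0 | 5% |
| ZOE-50 range, lower from 70 (96.6% vs 97.9%) | flat | 37.7% vs 27.2% | 1.0 to 2.1 | 5.3% to 6.9% |
| ZOE-50 range, higher from 70 | flat | 18.7% vs 27.2% | 0.8 to 1.7 | 5.4% to 6.4% |
| 97.2% below 70, 90.0%/89.1% from 70 | flat | 57.8% vs 27.2% | 3.1 to 6.1 | 8.2% to 20.4% |
| 97.2% below 70, 90.0%/89.1% from 70 | rising | 68.6% vs 37.3% | 3.1 to 6.3 | 7.8% to 19.4% |

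With rising incidence, the two ZOE-50 rows give at most 2.4 points and 7.2% false positives.

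**Step 4: after correction.** An age-stratified Mantel-Haenszel test rejects in 4.7% to 5.2% of samples in every scenario. Frequency-matching the cases on age and keeping the plain test gives 4.1% to 5.1%.

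**Step 5: scale.** With 100 per group, 80% power needs about 10% vs 25%, 20% vs 38%, or 50% vs 69.5%, that is, true differences of 15 to 20 points.

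**Step 6: timing.** With 7% and 15% as constant yearly censoring rates, a constant HZ hazard and 10 years of follow-up, the share of cases in years 5 to 10 is (e^−0.35 − e^−0.70)/(1 − e^−0.70) = 41% for vaccinated and (e^−0.75 − e^−1.50)/(1 − e^−1.50) = 32% for unvaccinated. Mean time to a case is about 4.4 vs 3.8 years.

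**The case against.** The strongest reply is that the age gradient comes from setting two trials side by side. The 97.2% is the overall ZOE-50 figure for adults 50 and older, and within that trial efficacy was nearly flat by age. On those figures the artefact is at most about 2 points. This stands: the documents point both ways, so they support saying that age could confound the comparison. A reader might infer that it would, and the documents do not carry that.

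The objective is also exploratory and descriptive, with no severity hypothesis or effect estimate, and even the steep scenario yields differences well below what 100 vs 100 can reliably detect. That limits the importance. It does not remove the point, because the plan attaches p-values to the contrast and the age shift biases the reported percentages as well.

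Three further readings are tempting and go too far:

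- That this is the only planned look at breakthrough severity. Section 8.1 plans adjusted relative risks of PHN among HZ cases, and exploratory objective 5 covers disseminated HZ in immunocompromised cases.
- That the cases are drawn unmatched. The protocol speaks only of a sample. The SAP is not available here and may hold the selection rule.
- That immune status adds to the bias by a known amount. The protocol gives no RZV efficacy in immunocompromised people, and the timing shift from censoring is only about 0.6 years.

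Finally, a crude description of how cases present is a legitimate aim. That stands, and it should be kept.

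**Conclusion.** The point holds in limited form. The planned tests are unadjusted, the protocol states no selection rule, and matching at the index date does not protect a comparison restricted to cases. If effectiveness falls with age as the cross-trial contrast suggests, about 58% of vaccinated and 27% of unvaccinated cases would be 70 or older. The plain test would then show a spurious difference of about 3 to 6 points and reject 8% to 20% of the time. If effectiveness is as flat as within ZOE-50, the effect is negligible.

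These sizes rest on the Table 1 age mix, on assumed age-specific rates of the clinical feature, and on assumed baseline incidence by age. The primary VE analyses are not affected. The case for acting is that the plan already contains the better method for the parallel PHN comparison.

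**What to change.** Keep the crude description of the 200 charts. Base the vaccinated vs unvaccinated comparison of severity and complications on results adjusted for age at HZ diagnosis, adding sex and immunocompromised status at diagnosis where numbers allow. Modified Poisson regression as in section 8.1, or an age-stratified Mantel-Haenszel test, would serve. State how the cases are selected, in the protocol or by reference to the SAP.

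Alternatively, frequency-match the unvaccinated cases to the vaccinated ones on age group only. Matching on age group, sex, immune status and calendar year together would be too fine for 100 cases. Supply is ample: 4 × 89,785 = 359,140 unvaccinated people at 10 per 1,000 person-years, with 15% yearly censoring taken as a constant rate, yield 359,140 × 0.01 × (1 − e^−1.6)/0.16, or about 18,000 HZ cases over 10 years.

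The cost is a sentence or two of text and a little more analysis, with no extra charts. Adjustment widens the intervals slightly. Matching means that the unvaccinated sample no longer represents all unvaccinated HZ cases.
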